Recent clinical reports have demonstrated excellent results utilizing high dose, short course radiation (or hypofractionated) therapy for prostate cancer. The typical treatment course lasts between 35 and 40 treatments for a course of definitive treatment for prostate cancer. Integrating the calculations suggested above, recent studies have evaluated using a definitive course of therapy in a much shorter time period with stereotactic body radiation therapy (SBRT). SBRT incorporates higher doses of radiation over a short time course. Recent publications by King and Boike demonstrate the increasing utility of this technology in the treatment of prostate cancer.^{6,7} King and colleagues demonstrated the safety and utility of a 5 day course of radiation therapy using the CyberKnife for SBRT treatment in a Phase I-II prospective study.⁶ The dose utilized was 7.25 Gy in 5 fractions. Grade 3 or greater rectal toxicity was seen in only 2 of 32 patients, and 78% of patients achieved a PSA nadir of ≤ 0.4 ng/mL at a minimum follow-up of 12 months. Boike and his colleagues in a separate Phase I-II study used three different dose regimens of 45 Gy, 47.5 Gy, and 50 Gy in 5 fractions.⁷ Grade 3 or greater GI toxicity was seen in $\leq 2\%$ of patients and grade 3 or greater GU toxicity was seen in $\leq 4\%$ of patients. The study noted 100% PSA control by the nadir + 2 ng/mL (ASTRO Phoenix) criteria with a short follow-up of 12-30 months. Both of these studies with short

followup suggest safe and successful treatment of prostate cancer with hypofractionated radiation utilizing SBRT.

A useful formalism in clinical radiation oncology is using the biologically equivalent dose (BED) equation to compare different fractionation schemes: $[(n \times d \times (1 + d/(\alpha/\beta))]$ where n=fraction number and d = dose per fraction. The table below compares the effective doses of different fractionation schemes based on the alpha/beta ratios discussed earlier. If the alpha/beta ratio for prostate is between 1.5-3.0, then the King regimen, 7.25 Gy x 5, should be at least as effective or more effective for *tumor control* than 90 Gy given in conventional 2 Gy fractions. Put in another way, if we assume an alpha/beta ratio of 1.5 for the prostate, as shown in the table below we would be able to deliver a BED of 211 Gy, as opposed to 187 Gy with standard fractionation (80 Gy in 2 Gy fractions).

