8.0 DATA ANALYSIS AND SPECIAL CONSIDERATIONS

8.1 Primary Analysis:

The primary objective is to estimate the 5-year biochemical failure free rate (BFFR) associated with the combined hypofractionated dose regimen and ADT. The BFFR is defined as a binary indicator whether PSA has increased by 2 ng/ml or more above the nadir PSA any time before the end of 5 years. The primary analysis will be performed by first obtaining the Kaplan-Meier (K-M) estimate of the biochemical failure free survival, and then estimating the 5-year biochemical failure free rate (BFFR) from this K-M curve together with 95% confidence interval. Greenwood formula will be used to calculate the variance of K-M estimate.

8.2 Secondary objectives:

8.2.1. Assess the incidence of grade 3 or greater late GU and GI toxicity and self-reported quality of life data.

Kaplan-Meier estimate of the incidence of grade 3 or greater late GU and GI toxicity will be constructed together with 95% confidence interval. Patient reported quality of life will be summarized using means and standard deviation for continuous measures, the contingency tables for categorical measures.

8.2.2 Assess clinical and pathologic control rates associated with the combined hypofractionated dose regimen and ADT.

Assessments will be performed 3 and 6 months after treatment and then every 6 months until 3 years, then annually until year 5. These rates will be estimated from Kaplan-Meier curves together with 95% confidence intervals.

Disease-Free Survival, measured from the date of enrollment to the date of documented progression or date of death using Kaplan-Meier estimates. Progression will be documented by PSA, bone scan, or biopsies.

Time to Local Progression (TLP) will be measured from the date of enrollment to the date of documented local progression using Kaplan-Meier estimates. Patients with new palpable abnormality on digital rectal examination or PSA failure at any point in time will also be offered biopsy to distinguish between local and distant failures. Patients who do not undergo biopsy will be censored at the last point of time they were considered locally controlled by digital rectal examination and PSA and considered not evaluable for further assessment.

Time to Distant Failure (TDF) will be measured from the date of enrollment to the date of documented metastatic disease. Patients who have negative biopsy following PSA failure or palpable abnormality will be considered to have only distant failure.

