8.3 Sample size

The primary endpoint is the 5-year biochemical failure free rate (BFFR) associated with the combined hypofractionated dose regimen and ADT. All patients will be followed for at least 5 years. We expect to observe 5-year BFFR 85% or higher. The annual dropout rate is expected to be at most 1% ~ 2% (or cumulative 5 year dropout rate is less than 10%). If 100 patients will finish 5 year follow up, the width of 95% confidence interval of BFFR will be less than 0.14. To incorporate the dropout rate, the total required sample size will be 110.

8.4 Safety monitoring.

An early stopping boundary will be used to test the hypotheses $H_0: Rt \leq 10\%$ versus $H_1: Rt > 10\%$ where Rt is the rate of grade 3 or greater on either GU or GI toxicity. We derive the one-sided stopping boundary using exact binomial test: at the first stage with 50 patients recruited, if 12 or more patients have experienced grade 3 or greater toxicity with an *attribution* of probably related (see section 10.2), the trial will be stopped. Otherwise, the trial will continue to recruit all 100 patients. If no more than 16 patients out of total 100 patients have experienced grade 3 or greater toxicity as detailed previously, the treatment is considered safe for further investigation. Based on EAST 5 (Copyright © 2009 Cytel Inc) Binomial one-sample exact test for single proportion, this stopping rule gives 87% power to reject unsafe treatment regime if the true toxicity rate is 20%.

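### Section 8.4 labels non-rejection of a 10% toxicity null as safe for further investigation, although a result at the cutoff (16 of 100) does not exclude the plan's own unsafe rate of 20%

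*Combined protocol and SAP*

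**What the plan says.** Section 8.4 (Safety monitoring) sets a two-look rule on Rt, "where Rt is the rate of grade 3 or greater on either GU or GI toxicity". The null is Rt at most 10% and the alternative is Rt above 10%. On the method it says: "We derive the one-sided stopping boundary using exact binomial test".

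- **First look:** the trigger reads "at the first stage with 50 patients recruited, if 12 or more patients have experienced grade 3 or greater toxicity". Only events judged probably related to treatment are counted. Once the trigger is met, accrual ends; below it, the study carries on to its full 100.
- **Final look:** with no more than 16 of 100 patients having such an event, "as detailed previously, the treatment is considered safe for further investigation".
- **Operating characteristics:** 87% power to reject an unsafe regimen at a true rate of 20%, credited to a commercial design package. No type I error is stated, and no figure is given for rates between 10% and 20%.

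Section 8.2.1 separately plans an estimate for late toxicity: "Kaplan-Meier estimate of the incidence of grade 3 or greater late GU and GI toxicity will be constructed together with 95% confidence interval". Section 8.4 does not refer to it.

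**The concern.** The test is built to detect excess toxicity, and as a stopping boundary that is a sensible construction. The difficulty is the conclusion attached to not crossing it. With acceptable toxicity as the null, non-rejection means only that the data did not prove a rate above 10%. Section 8.4 turns this into a favourable statement about safety without asking that an upper confidence limit fall below 10%, 20% or any other value.

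At stake is what the trial may say about toxicity after 100 patients. An observed 16% is 1.6 times the limit in the null hypothesis, and it would still carry the favourable label. A reader of the report could take that label as evidence that toxicity is within the limit.

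**Working it through.** **Inputs, all from section 8.4.** First look at 50 patients, stop at 12 or more events. Final look at 100 patients, favourable label at 16 or fewer, so rejection at 17 or more. Null limit 10%; unsafe rate 20%; stated power 87%. The 15% rate used below is an assumption of this review; the results are shown over a range around it.

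**Formula.** With p the true rate of counted events:

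P(label) = sum over k = 0 to 11 of Bin(k; 50, p) × P(Bin(50, p) ≤ 16 − k), and P(reject) = 1 − P(label).

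**1. The plan's own figure.** At p = 0.20:

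- rejection at the first look: 28.9%
- rejection at the final look: 52.1%
- total power: 81.0%, against 87% stated.

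Variants at p = 0.20:

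| Variant | Power |
|---|---|
| One look only, reject at 17 or more of 100 | 80.8% |
| First-look boundary 11 instead of 12 | 81.6% |
| First-look boundary 13 instead of 12 | 80.8% |
| Final boundary 18 or more of 100 | 73.6% |
| Final n = 110 (the section 8.3 total), reject at 17 or more | 90.9% |
| Final boundary 16 or more of 100 | 87.2% |

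Of these, only the last reproduces 87%, and it contradicts the text, under which 16 events still earn the favourable label. The two statements differ by one event.

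**2. How often the label is given.**

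| True rate | Cutoff as written (label at ≤ 16) | Cutoff that reproduces 87% (label at ≤ 15) |
|---|---|---|
| 10% | 97.8% | 95.9% |
| 12% | 91.0% | 85.7% |
| 15% | 66.8% | 56.7% |
| 17% | 45.4% | 35.3% |
| 20% | 19.0% | 12.8% |

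From the first column, the type I error at 10% is 100 − 97.8 = 2.2%. At 15% the written rule stops 6.3% of trials at the first look and rejects 26.9% at the final look, which leaves 66.8% with the label.

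**3. What a labelled result can exclude.** The Clopper-Pearson two-sided 95% interval for x of n is Beta(0.025; x, n − x + 1) to Beta(0.975; x + 1, n − x). For 16 of 100 this is Beta(0.025; 16, 85) = 9.4% to Beta(0.975; 17, 84) = 24.7%. For 15 of 100, the largest labelled count under the other cutoff, it is 8.6% to 23.5%. Both intervals contain 20%. They are ordinary fixed-sample intervals, with no adjustment for the first look.

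**The case against.** The strongest defence is that this is a standard go/no-go rule with two design points, 10% and 20%. The error of passing an unsafe regimen is addressed at 20%, where the stated power implies 13%. A rate of 15% lies midway, where any rule of this size gives an intermediate probability. The full phrase also speaks of further investigation, which is milder than a claim that toxicity is shown to be at most 10%. Late toxicity is to be estimated with an interval under 8.2.1, and a Safety Monitoring Committee reviews the trial annually.

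Much of this stands. The boundary is acceptable for stopping. The 66.8% at 15% is an operating characteristic and not in itself a failure, although 15% does lie inside the plan's alternative. The qualifier does soften the label. It does not supply the missing evidence, because a labelled result can still include 20%. The 8.2.1 interval covers late events only and is not tied to the 8.4 verdict.

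Three stronger readings are tempting, and the documents do not support them:

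- *That 8.4 is the trial's only formal decision rule.* The safety run-in in section 6.1 has its own: with 0 or 1 dose-limiting toxicity in six patients the regimen passes, otherwise the trial stops.
- *That a labelled regimen could be several times as toxic as the rationale suggests.* Section 1.0 gives GI rates of at most 2% and GU rates of at most 4% in the higher-dose study. It also reports grade 3 or greater rectal toxicity in 2 of 32 patients (6.25%) at this trial's own dose, so about 6% is not a ceiling on the rationale's rates.
- *That the favourable side of the rule is uncontrolled.* It is controlled at 20%, though less tightly as written than as stated.

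**Conclusion.** The point holds for the inference in 8.4, and the boundary can remain a stopping rule. Non-rejection supports the statement that the boundary was not crossed. It does not support a positive statement about safety: a result at the cutoff has an exact 95% interval of 9.4% to 24.7%, and a regimen at the plan's own unsafe rate receives the label 19.0% of the time under the written rule (12.8% under the cutoff that matches the stated power). The criticism therefore stands whichever cutoff was intended.

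Separately, the cutoff of 16 and the stated 87% power are inconsistent: 81.0% follows from the text.

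These figures assume independent patients with a common rate, both looks taken at exactly 50 and 100 patients, and complete counting of events at each look. All rates refer to counted events, meaning those with the required attribution, so they are not rates of all grade 3 or greater events. The choice of 15% affects only the illustration. A reader might infer that the trial would declare a toxic regimen safe without qualification; the text is limited to further investigation and does not go that far.

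**What to change.** 1. In 8.4, replace the favourable conclusion with: *the toxicity boundary was not crossed; a rate above 10% was not demonstrated.* Report beside it the observed rate of grade 3 or greater GU or GI toxicity (events attributed as probably related) with its exact 95% confidence interval.
2. Reconcile the final cutoff with the stated power, and state the type I error of the rule that results. The documents do not show which of the two figures is in error.

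The cost is a change of wording, one exact interval and a check of the design output. No patients, visits or data are added. The drawback is a less favourable statement whenever the boundary is not crossed.

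A positive claim tied to a bound is optional and is not part of the correction. For example, a one-sided 95% exact upper limit below 20% would need 13 or fewer events in 100 (upper limit 19.9%). Both the bound and the confidence level are matters of judgement. With the same first look, a regimen at 15% would still pass 34.7% of the time, and one at 10% would pass 87.6% of the time instead of 97.8%.

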9.0 ACCRUAL AND STUDY DURATION

Of approximately 90 patients per month seen in consultation for prostate cancer each month in the department of radiation oncology (East Baltimore, Green Spring Station, Sibley and Suburban sites total), we anticipate approximately 25% of patients to be eligible. All eligible patients will be offered enrollment on the study, and we estimate a 30% accrual rate with 5% dropout rate, resulting in an average of at least 7 patients enrolled per month. The planned study open date is June 2013 for the East Baltimore site and May 2014 for Sibley and Suburban sites. The projected closure date of accrual is August 2015. The total length of the study would be from June 2013-August 2020.

10.0 REPORTING OF ADVERSE EVENTS

10.1 General

Adverse event collection and reporting is a routine part of every clinical trial. This study will use the descriptions and grading scales found in the NCI Common Terminology Criteria for Adverse Events version 4.0 (CTCAE v 4.0) and the LENT-SOMA criteria.¹⁴ The CTCAE v 4.0 is available at <http://ctep.cancer.gov/reporting//ctc.html>.

Information on all adverse events, whether reported by the participant, directly observed, or detected by physical examination, laboratory test or other means, will be collected, recorded, followed and reported as described in the following sections.

Adverse events experienced by participants will be collected and recorded from initiation of study, throughout the study, and within 5 years post radiation therapy. Participants who experience an ongoing adverse event related to a study procedure beyond 5 years post RT will continue to be contacted by a member of the study team until the event is resolved, stabilized, or determined to be irreversible by the participating investigator.

Participants should be instructed to report any serious post-study event(s) that might reasonably be related to participation in this study. The investigator should notify the IRB and any other applicable regulatory agency of any unanticipated death or adverse event occurring after a participant has discontinued or terminated study participation that may reasonably be related to the study.

10.2 Definitions

Adverse Event (AE): An adverse event is any undesirable sign, symptom or medical condition or experience that develops or worsens in severity after starting the first dose of study treatment or any procedure specified in the protocol, even if the event is not considered to be related to the study.

Abnormal laboratory values or diagnostic test results constitute adverse events only if they induce clinical signs or symptoms or require treatment or further diagnostic tests.

Serious Adverse Event: means an event that is

- fatal
- life-threatening
- persistent or significantly disabling or incapacitating
- inpatient hospitalization or prolongation of hospitalization

- congenital anomaly or defect and/or
- a significant medical incident (considered to be a serious study related event because, based upon appropriate medical judgment, it may jeopardize the subject and may require medical or surgical intervention to prevent one of the outcomes listed in this definition.)

Events not considered to be serious adverse events are hospitalizations for:

- routine treatment or monitoring of the studied indication, not associated with any deterioration in condition, or for elective procedures
- elective or pre-planned treatment for a pre-existing condition that did not worsen
- emergency outpatient treatment for an event not fulfilling the serious criteria outlined above and not resulting in inpatient admission
- respite care

Important Adverse Event: means an event, although not a Serious Adverse Event, which still presents an undesirable occurrence that interferes with the subject's usual activities and may be persistent or require treatment. (For example, serious rash, cough, or fever.)

Expectedness:

- Expected: Expected adverse events are those that have been previously identified as resulting from administration of protocol intervention. For the purposes of this study, an adverse event is considered expected when it appears in the current adverse event list, package inserts or is included in the informed consent document as a potential risk.
- Unexpected: An adverse event is considered unexpected when it varies in nature, intensity or frequency from information provided in the current adverse event list, package inserts or when it is not included in the informed consent document as a potential risk

Attribution is the relationship between an adverse event or serious adverse event and the study treatment. Attribution will be assigned as follows:

- Definite – The AE is clearly related to the study treatment.
- Probable – The AE is likely related to the study treatment.
- Possible – The AE may be related to the study treatment.
- Unlikely - The AE is doubtfully related to the study treatment.
- Unrelated - The AE is clearly NOT related to the study treatment.

10.3 Reporting Procedures

10.3.1 General

All adverse events will be captured on the appropriate study-specific case report forms (CRFs).

10.3.2 All **fatal** events, both **expected and unexpected**, must be reported to the JHM IRB within a time period as specified by current institutional guidelines after the PI learns of the event, whether or not the PI believes the event to be related to the study. All other events, which are both **serious** and **unexpected**, must be reported to the JHMI IRB within a time period as specified by current institutional guidelines after the PI learns of the event. Events which are **serious** but **expected**, should be reported as part of the continuing review

application. If any of these Serious Adverse Events requires a change to the protocol or consent form, the PI must make those changes promptly and submit the revised documents to the JHM IRB.

10.3.3 Important Adverse Events that are **unexpected** must be reported to the JHM IRB within a time period as specified by current institutional guidelines. If the Important Adverse Event requires changes to the protocol or consent form, the PI must make those changes promptly and submit the revised documents to the JHM IRB.

10.3.4 All other **unexpected** Adverse Events or changes to the protocol and consent form must be reported to the JHM IRB, within a time period as specified by current institutional guidelines

10.4 Following a Study Related Adverse Event

If a patient experiences an adverse event while on study, the following steps will be taken:

- 1) Establish the cause and severity of the adverse event and determine if said event is related to study participation.
- 2) Principal Investigator will decide what treatment(s), if any, is/are required.
- 3) Depending on the type and severity of adverse event, an appropriate follow-up schedule will be constructed which will allow for determination of event outcome.
- 4) Patient will be followed by principal investigator until the adverse event has resolved.

11.0 DISPOSITION OF DATA

Clinical records for all subjects studied including history and physical findings, laboratory and clinical data, and operative and dosimetric records are to be maintained by the investigators in a secure location at Johns Hopkins Cancer Center. Any records that are stored electronically will be password protected and only those who are involved in the research will have a password. These records are to be stored for a minimum of 8 years after last clinical visit.

12.0 PROTOCOL MODIFICATIONS

All revisions or amendments (that are not required for immediate patient safety) to the protocol must be approved by the Johns Hopkins Institutional Review Board prior to implementation.

13.0 DEPARTURES FROM PROTOCOL

If there is a departure from the Clinical Protocol, the Principal Investigator will notify in writing the local IRB at Johns Hopkins at the time of annual review (continuing review). The research coordinator will keep a log of all deviations/departures that occur on this project and this log will be reviewed by the research team on a monthly basis. During the review the research team will discuss corrective action plans to minimize future deviations/departures. If there are departures to the protocol that effects patient safety the principal investigator will notify in writing the IRB within 24 hours of discovering the departure/deviation.

14.0 CRITERIA FOR WITHDRAWAL FROM STUDY

Patients may be withdrawn from the study for the following reasons:

- a) Consent for participation is withdrawn
- b) Noncompliance to study procedures

- c) Development of intercurrent, non-cancer related illness that prevents either continuation of therapy or regular follow-up.

15.0 ROLES AND RESPONSIBILITIES OF STUDY PERSONNEL

Principal Investigator: Oversees all aspects of the trial. Recruits and consents patients and administers protocol specific procedures. Provides medical care to research subjects during the conduct of the study. Follows and advises regarding the treatment of adverse events. Reports SAE's to the IRB within the required time frame. Amends the trial as necessary to reflect unforeseen adverse events, new scientific data and for the general integrity of the study. Monitors the trial. Is ultimately responsible for the conduct of protocol.

Co-Investigators: If a physician: can recruit and consent patients and can administrate protocol specific procedures. Can provide medical care to research subjects during the conduct of the study. Has input on the course of action for adverse events.
If not a physician: Collaborates with the Principal Investigator according to area of expertise.

Research Nurses: Executes protocol specific procedures requiring nursing qualifications. Provide nursing care to research subjects during the conduct of the study. May consent patients for study enrollment.

Data Manager/Study Coordinator: Collects data from subject's medical records and codes it onto the study's case report forms. Notifies principal investigator of any deviations that he/she finds while managing the data. Prepares annual IRB renewals and termination report upon study completion, assists with management of regulatory issues governing the trial. Monitors the trial.

